## 8.6. TAVR Implant Procedure

The implantation procedure is performed according to the standard procedures of the implanting physicians. In countries where required, including the United States, the local heart team's interventional cardiologist(s) and cardiac surgeon(s) must jointly participate in the intra-operative technical aspects of the TAVR procedure. Procedural aspects specific to the Medtronic TAVR system should be performed according to the Instructions for Use. The following variables will be collected regarding the TAVR implantation procedure:

- Name of the primary and secondary operator
- Anesthesia type (general or local)
- Delivery catheter access site and vessel diameter of access site
- Use of EnVeo InLine Sheath alone, OR use of separate introducer sheath size and type
- Pre-deployment BAV (yes/no)
- Use of rapid pacing during BAV and deployment (yes/no)
- Size of TAV implanted
- Post-implant dilation (yes/no)
- Post-implant pressures at final result (LV systolic and end-diastolic, aortic systolic and diastolic)
- Implantation of TAV within the desired location (yes/no)
- Post-implant degree of prosthetic regurgitation by angiography (Sellers criteria, 45)
- Post-implant degree of prosthetic paravalvular regurgitation by TEE, if performed
- Post-implant degree of prosthetic transvalvular regurgitation by TEE, if performed
- More than one TAV implanted (yes/no)
- Patency of coronary arteries post-implant (yes/no)
- Estimated contrast volume used
- Total procedural time(minutes): time in procedure room to exit from procedure room
- Information on use of resheath/recapture feature (Definitions of resheath/recapture use are provided in Appendix IV)
- Occurrence of adverse events
- If TAV implantation not attempted, reason why

## 8.7. Post-Implant Anti-thrombotic Therapy

The recommended post implant anti-thrombotic regimen for TAVR subjects will be 30 days or more of Dual Anti-Platelet Therapy (DAPT) followed by aspirin through 12 months.

## 8.8. Clinical Assessment

Clinical assessment is required at the following post-implant intervals: discharge, 30 days, 1 year, 2 years, 3 years, 4 years, 5 years, 7 years and 10 years. The following variables will be documented at each protocol-required follow-up interval:

- Follow-up status
- NYHA functional classification (except at discharge)
- Modified Rankin Score (except at years 6 through 10)
- Prescribed antithrombotic medications (except at years 6 through 10)
- KCCQ (except at discharge and years 6 through 10)
- EQ-5D (except at discharge, and years 2 through 10)
- Documentation of any adverse events (adverse events will be collected via telephone at 6-year, 8-year, and 9-year visits)

## 8.9. Assessment of Safety

Definitions, procedures of evaluation, documentation and reporting of adverse events and device deficiencies are presented in section 10.0 Adverse Events and Device Deficiencies.

## 8.10. Echocardiography

Transthoracic echocardiography (TTE) is required at the following intervals: pre-implant, 18 hours to 7 days (for device success), 30 days, 1 year, 2 years, 3 years, 4 years, 5 years, 7 years and 10 years. Exams will be sent to the Echo Core Lab for central assessment. Further details of the echocardiography methods are provided in APPENDIX I: ECHOCARDIOGRAPHY PROCEDURES. Sites will acquire the necessary views and measurements for the Echo Core Lab to assess the following variables at each protocol-required exam:

- Height (cm or in) and weight (kg or lb)
- Heart rate
- Left ventricular outflow tract (LVOT) diameter in mid systole
- Max aortic/prosthetic valve velocity ( $V_2$ ) by CW Doppler
- Aortic valve velocity time integral (VTI) by CW Doppler
- Mean gradient across aortic valve ( $MGV_2$ ) by CW Doppler
- LVOT VTI by PW Doppler
- Grade of aortic/prosthetic transvalvular regurgitation )
- Grade of aortic/prosthetic paravalvular regurgitation (post-implant only)
- Grade of prosthetic total (transvalvular plus paravalvular) regurgitation (post-implant only)
- Grade of mitral regurgitation
- Grade of tricuspid regurgitation
- Max tricuspid regurgitant (TR) jet velocity (if TR is present)
- Left ventricular internal dimension at end diastole

- Left ventricular internal dimension at end systole
- Interventricular septal thickness at end diastole
- Left ventricular posterior wall thickness at end diastole
- Left atrial diameter (anterior-posterior linear dimension) at systole
- Left ventricular ejection fraction
- Grade of diastolic dysfunction (if present)

In addition, the following variables will be derived by the central database from the appropriate measurements reported by the site:

- Body surface area (Dubois and Dubois, [39])
- Peak aortic pressure gradient
- Aortic valve area (AVA)/effective orifice area (EOA) by continuity equation
- Aortic valve area index (AVAI)/effective orifice area index (EOAI)
- Doppler Velocity Index (DVI)
- Estimated right ventricular systolic pressure (RVSP)

Derived variables may be displayed on the eCRF upon entry of the appropriate raw measurements. The pre-implant qualifying AVA or AVAI must be based on the site reported variables for LVOT diameter, LVOT VTI, aortic valve VTI, height, and weight.

## 8.11. Missed Follow-up Visits

Every effort should be made to ensure subjects return to the clinic for all protocol required follow-ups, with the exception of the 6, 8 and 9-year follow-up visits which may be conducted remotely (eg, phone call). If the subject is unable to return for an in-person clinic visit, the Investigator, or designee, should document in the subject record the reason the subject was unable to complete the visit and, if applicable, follow the requirements for deviation reporting as outlined in section 8.14 Deviation Handling.

The investigator should also make every effort to contact the subject within the visit window to collect the subject's vital status as well as information related to potential adverse events, safety data, and hospitalizations.

## 8.12. Unscheduled Follow-up Visits

If a subject returns to the study site or is contacted via telephone between their scheduled follow-up visits for an event potentially related to a study endpoint, the visit or telephone call will be treated as an unscheduled follow-up, and the assessments completed at this visit will be conducted at the discretion of the investigator.

## **8.13. Recording Data**

### **8.13.1. Data Collection**

Study sites will assign a unique ID number to each subject. Records of the subject/subject ID relationship will be maintained by the study site. Individual subject medical information obtained as a result of this study will be considered confidential.

This study will utilize an Oracle Clinical Remote Data Capture (RDC) system that is the property of Medtronic. Required data will be recorded on electronic case report forms (eCRFs) by authorized site personnel as indicated on the Delegation Task List (DTL). Study personnel delegated for eCRF completion and/or approval per the DTL will be trained on the use of the RDC system and thereafter provided with a username and password to access the system. The eCRFs must be completed and/or updated to reflect the latest observations on the subjects participating in the study. The investigator (or approved sub-investigator) will approve the eCRFs by electronically signing the appropriate pages of each eCRF.

Data from the core lab will be entered into the Oracle Clinical RDC system by core lab personnel per their procedures established for the study. The core lab cardiologist will approve core lab eCRFs.

The Oracle Clinical RDC system maintains an audit trail of entries, changes, and corrections in eCRFs. If a person only authorized to complete eCRFs makes changes to an already signed eCRF, the investigator shall re-approve this eCRF.

All study-related documents must be retained until notified by Medtronic that retention is no longer required. Medtronic will inform the investigator/institution when these documents are no longer required to be retained.

No study document or image should be destroyed without prior written agreement between Medtronic and the investigator. Should the investigator wish to assign the study records to another party or move them to another location, advance written notice must be given to Medtronic.

### **8.13.2. Time Windows for Completion and Submission of eCRFs**

The Device Use Notification eCRF should be completed as soon as possible after device use. Effort should be made for all other eCRFs to be completed and approved within 3 weeks of the applicable follow-up visit.

### **8.13.3. Data Review and Processing**

Medtronic will be responsible for the processing and quality control of the data. Data review, database cleaning and issuing and resolving data queries will be done according to Medtronic internal SOPs and the Data Management Plan for this study. The study database will be developed and validated per the Data Management Plan for this study, and will employ validation programs (eg, range and logic checks) on entered data to identify possible data entry errors and to facilitate data validation. The study database will maintain an audit trail of all changes made to the eCRFs.

#### **8.13.4. Source Documents**

Entered data must be traceable to source documents. Source documentation is defined as the first time the data appear and may include all clinical records, hospital records, procedural reports, autopsy reports, and any other material that contains original information used for study data collection or adverse event reporting. Identified discrepancies between source documents and the eCRFs will be resolved through the online query resolution process per the Data Management plan.

The eCRFs may not serve as source documents. Source documentation for data elements not routinely captured in medical records (echocardiography variables, MDCT variables, catheterization, procedural data variables, local heart team assessment, Modified Rankin Score) may vary from center to center; therefore, the site may use technical worksheets if identified as source documents.

Source documents must be retained by the investigational site and made available for monitoring or auditing by the sponsor's representative or representatives of the FDA and other applicable regulatory agencies or IRB/EC.

The investigator must ensure the availability of source documents from which the information on the eCRFs was derived. Where printouts of electronic medical records are provided as source documents, or where copies of source documents are retained as source documents, they should be signed and dated by a member of the investigation site team indicating they are a true reproduction of the original source document.

Copies of source documents may be requested to support event adjudication by the Clinical Events Committee. In some geographies, availability of source documentation may be limited due to institutional policies. If a specific source document is not available, necessary information may be transcribed onto the relevant eCRF page.

In addition, the medical records of study subjects should be marked or flagged in such a way to indicate their participation in the study.

#### **8.13.5. Subject Confidentiality**

All information and data sent to parties involved in study conduct concerning subjects or their participation in this study will be considered confidential. Study sites will assign a unique subject ID number (SID) to each subject. Records of the subject/SID relationship will be maintained by the study site. The SID is to be recorded on all study documents to link them to the subject's medical records at the site. To maintain confidentiality, the subjects' name or any other personal identifiers should not be recorded on any study document other than the informed consent form. In the event a subject's name is included for any reason, it will be masked as applicable. In the event of inability to mask the identification (eg, digital media), it will be handled in a confidential manner by the authorized personnel.

## 8.14. Deviation Handling

A protocol deviation is defined as an event where the clinical investigator or site personnel did not conduct the study according to the protocol or the Investigator Agreement. Examples of protocol deviations include but are not limited to the following:

- Failure to obtain informed consent prior to participation
- Incorrect version of the informed consent form used
- Failure to obtain IRB approval before the start of the study
- Implanted subject did not meet inclusion/exclusion criteriai
- Required testing and/or measurements not done or incorrectly done
- Subject does not attend follow-up visit or follow-up visit outside window
- Unauthorized use of investigational devices
- Adverse events not reported in the required time frame as required by regulation or as specified in the CIP
- Control of study devices not maintained
- Source data permanently lost
- Enrollment of patients during lapse of IRB approval

Investigators should obtain prior approval from Medtronic before initiating any change or deviation from the CIP, except where necessary to protect the life or physical well-being of a subject in an emergency situation. Such approval shall be documented in writing and maintained in the Investigator Site File. Prior approval is generally not expected in situations where unforeseen circumstances are beyond the investigator's control (eg, subject did not attend scheduled follow-up visit).

Deviations will be reported to Medtronic regardless of whether medically justifiable, pre-approved by Medtronic, or taken to protect the subject in an emergency. Study deviations should be reported to Medtronic via the Study Deviation eCRF (one eCRF for each protocol deviationii).

Investigators should report the following deviations to Medtronic and their reviewing IRB/EC within 5 working days of the occurrence of the deviations:

- Failure to obtain written informed consent
- Deviations to protect the life or physical well-being of a subject in an emergency

In addition, investigators are required to adhere to local IRB/EC procedures for reporting deviations.

Deviations are analyzed, their significance is assessed, and any corrective and/or preventative actions that maybe warranted are identified. Medtronic is responsible for analyzing deviations, assessing their

---

i Subjects must meet all inclusion/exclusion criteria to be eligible for implantation. However, it will not be considered a protocol deviation if study related testing (eg, echo, MDCT, labs, coronary arteriography, Heart Team assessment, or Screening Committee assessment) of a consented subject identifies implantation eligibility criteria that are not met.

ii In the case of a missed study visit (eg, followup visit), completion of only one protocol deviation eCRF is sufficient and additional eCRFs are not required for each assessment missed at that visit.

significance, and identifying any corrective and/or preventive actions that may be warranted. Repetitive or serious investigator compliance issues may represent a need to initiate a corrective action plan, which may include suspension of enrollment or termination of the investigator's or site's participation in the study.

## **8.15. Subject Withdrawal or Discontinuation**

All subjects will be encouraged to remain in the study through the last follow-up visit at 10 years. Subjects who discontinue participation prematurely will be included in the analysis of results (as appropriate) and will not be replaced in the enrollment of total study subjects. If a subject is discontinued from the study early, the reason for discontinuation should be documented in the subject file and a Study Exit eCRF must be completed.

The study site will make every effort to have all subjects complete the follow-up visit schedule. A subject will not be considered lost to follow-up unless all efforts to obtain compliance are unsuccessful. At a minimum, the effort to obtain follow-up information must include 3 attempts to make contact via telephone or e-mail and if contact via these methods is not successful, a traceable letter from the investigator should be sent to the subject's last known address. Should telephone, e-mail and mail efforts to contact the subject be unsuccessful, the subject's primary physician should be contacted. Subjects will then be deemed lost to follow up. All contact efforts to obtain follow-up must be documented in the subject's medical records.

If a subject discontinues the study at any time, is withdrawn from the study early, or completes all protocol required follow-up they should continue to be followed by the implanting site according to their routine clinical practice for aortic valve patients. If, for any reason, this is not possible for a particular subject, or if subject needs to change their follow-up site at any time point after conclusion of the study, investigators should refer subjects to a local site with appropriate training and experience in managing patients with implanted aortic valves.

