6.2. Sample Size

This study will involve 150 subjects with an attempted implant with the Medtronic TAVR system. The primary analysis will be performed when 150 consecutive subjects with an attempted implant have had the chance to complete 30-day follow-up.

This is not a hypothesis-driven study, therefore the sample size of 150 for the analysis was not determined by statistical sample size methods. However, a sample size of 150 subjects is adequate for a descriptive assessment of the procedural safety and efficacy of the Medtronic TAVR system in subjects with bicuspid aortic valves. Table 2 provides the level of precision with

the 95% confidence intervals around possible endpoint rates in bicuspid subjects at sample sizes of 150 subjects (assuming that when occurred, the endpoint rates in bicuspid subjects are similar to those in the historical data from tricuspid subjects). The rates provided are based on the weighted average from historical data presented in Table 1.

Table 2. Confidence intervals for sample sizes of 150 subjects.

Endpoint	Possible Rate in Bicuspid Subjects (n) ¹	Sample Size	95% Exact Binomial Confidence Interval
All-cause mortality or disabling stroke at 30 days	2.7% (4)	150	0.7%, 6.7%
Device success	94.7% (142)	150	89.8%, 97.7%

¹Rate values from the weighted average of the historical data are rounded up to correspond to the nearest whole number for subjects with an endpoint for sample sizes of 150; n denotes number of subjects with an endpoint.

7. Statistical Methods

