7.4. Handling of Missing, Unused, and Spurious Data and Dropouts

Every effort will be undertaken to minimize missing data. In time-to-event outcomes drop-outs will be censored at the time of discontinuation, consistent with the Kaplan-Meier approach.

Missing (accidentally, due to withdrawal, missing follow-up or loss to follow-up, etc.), unused and spurious data will remain identifiable in the database. Data from subjects that cannot be analyzed for a specific variable will be displayed as missing in the relevant summary tables. In this manner, all data for a specific variable are accounted for. Unless otherwise specified, no statistical techniques will be used to impute missing data. The number of subjects included in each analysis will be reported so that the reader can assess the potential impact of missing data.

In the case of partial dates, if only the month and year are known, the event or assessment will be analyzed as if it occurred on the 15th of that month. If only the year is known, the event or assessment will be analyzed as if it occurred on June 30th of that year. These resolutions of partial dates are subject to the restrictions that events must occur no earlier than the procedure date.

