7.9.3. Additional Outcome Measures

1. All-cause mortality at one year, and annually through 10 years

Event rate estimates will be provided at 1 year and annually thereafter up to 10 years for the attempted implant set. The outcome is descriptive including Kaplan-Meier rates and no statistical hypothesis test is specified.

2. All stroke (disabling and non-disabling) at one year, and annually through 10 years

Event rate estimates will be provided at 1 year and annually thereafter up to 10 years for the attempted implant set. The outcome is descriptive including Kaplan-Meier rates and no statistical hypothesis test is specified.

3. New permanent pacemaker implantation at 30 days

Event rate estimates will be provided at 30 days for the attempted implant set. The outcome is descriptive including Kaplan-Meier rates and no statistical hypothesis test is specified.

4. Myocardial Infraction at 30 days

Event rate estimates will be provided at 30 days for the attempted implant set. The outcome is descriptive including Kaplan-Meier rates and no statistical hypothesis test is specified.

5. Life-threatening bleeding at 30 days, one year, and annually through 10 years

Event rate estimates will be provided at 30 days, 1 year and annually thereafter up to 10 years for the attempted implant set. The outcome is descriptive including Kaplan-Meier rates and no statistical hypothesis test is specified.

6. Prosthetic valve endocarditis at 30 days, one year, and annually through 10 years

Event rate estimates will be provided at 30 days, 1 year and annually thereafter up to 10 years for the attempted implant set. The outcome is descriptive including Kaplan-Meier rates and no statistical hypothesis test is specified.

7. Prosthetic valve thrombosis at 30 days, one year, and annually through 10 years

Event rate estimates will be provided at 30 days, 1 year and annually thereafter up to 10 years for the attempted implant set. The outcome is descriptive including Kaplan-Meier rates and no statistical hypothesis test is specified.

8. Valve-related dysfunction requiring repeat procedure at 30 days, one year, and annually through 10 years

Event rate estimates will be provided at 30 days, 1 year and annually thereafter up to 10 years for the attempted implant set. The outcome is descriptive including Kaplan-Meier rates and no statistical hypothesis test is specified.

9. Repeat hospitalization for ascending aorta disease at 30 days, one year, and annually through 10 years

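### No vital-status check is described after a subject is lost or withdraws, so 10-year Kaplan-Meier mortality is unbiased only if leavers die at the same rate as stayers

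*Protocol*

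**What the plan says.** Protocol 8.15 sets minimum steps before a subject counts as lost: three telephone or e-mail attempts, a traceable letter, then the primary physician. The closing rule reads: "Should telephone, e-mail and mail efforts to contact the subject be unsuccessful, the subject's primary physician should be contacted. Subjects will then be deemed lost". For early discontinuation the reason is documented and "a Study Exit eCRF must be completed". The implanting site should go on seeing such patients in routine practice, but this is not described as study data. Protocol 10.2.1 has adverse events documented from enrolment until exit, and deaths are entered on the adverse event form.

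The one explicit vital-status instruction is in Protocol 8.11. It covers missed visits, where the investigator should "make every effort to contact the subject within the visit window to collect the subject's vital status".

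On the analysis side, SAP 7.9.3 item 1 (all-cause mortality) states: "Event rate estimates will be provided at 1 year and annually thereafter up to 10 years for the attempted implant set". SAP 7.4 censors drop-outs at discontinuation and adds: "Unless otherwise specified, no statistical techniques will be used to impute missing data". Neither document describes a records search after closure or a sensitivity analysis for informative drop-out.

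**The concern.** Kaplan-Meier treats a censored subject as having the same future risk as those still under observation. Over 10 years in patients aged 60 and over, leaving a study may well be related to health, and someone who answers neither telephone, e-mail nor letter may already have died. If the physician does not know of the death, that subject is censored alive at last contact, and no described route brings the death into the database later.

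All-cause mortality is the first additional outcome and feeds the final report. Protocol 5.2 assumes, rather than shows, that outcomes after the procedural period resemble those in tricuspid patients; the long follow-up is this study's direct evidence on that. Mortality is also the outcome easiest to complete without a visit.

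**Working it through.** **Figures in the plan.** The documents state no 10-year mortality, attrition rate or long-term precision, so there is nothing to reproduce on this point. The only stated precision (SAP Table 2) concerns the 30-day safety endpoint and device success. It reproduces (4/150 gives 0.7% to 6.7%; 142/150 gives 89.8% to 97.7%) but has no bearing here.

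**Inputs.** n = 150 (SAP 6.2: "This study will involve 150 subjects with an attempted implant with the Medtronic TAVR system") and horizon T = 10 years (SAP 7.9.3). Assumed, not in the documents: constant death hazard h while in the study, constant loss hazard c, and hazard r×h after loss.

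**Formulas.**
- Kaplan-Meier limit: 1 − exp(−hT).
- Leaving alive by year 10: c/(h+c) × [1 − exp(−(h+c)T)].
- True survival: exp(−(h+c)T) + c·exp(−rhT)·[1 − exp(−kT)]/k, with k = h + c − rh. The first term is those who stay and survive; the second is those who leave and survive.

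**Case A: h = 0.03, c = 0.02.** Kaplan-Meier gives 1 − exp(−0.3) = 25.9%. Leavers are 0.02/0.05 × (1 − exp(−0.5)) = 15.7%, about 24 of 150. The stay-and-survive term is exp(−0.5) = 0.6065.

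| r | leave-and-survive term | true 10-year mortality | true minus Kaplan-Meier (points) |
|---|---|---|---|
| 0.5 | 0.1452 | 24.8% | −1.1 |
| 1 | 0.1343 | 25.9% | 0 |
| 1.5 | 0.1244 | 26.9% | +1.0 |
| 2 | 0.1154 | 27.8% | +1.9 |
| 3 | 0.1000 | 29.3% | +3.4 |

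**Case B: h = 0.05, c = 0.04.** Kaplan-Meier gives 1 − exp(−0.5) = 39.3%. Leavers are 0.04/0.09 × (1 − exp(−0.9)) = 26.4%, about 40 of 150. The stay-and-survive term is exp(−0.9) = 0.4066.

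| r | leave-and-survive term | true 10-year mortality | true minus Kaplan-Meier (points) |
|---|---|---|---|
| 0.5 | 0.2291 | 36.4% | −2.9 |
| 1.5 | 0.1755 | 41.8% | +2.5 |
| 2 | 0.1548 | 43.9% | +4.5 |
| 3 | 0.1223 | 47.1% | +7.8 |

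Differences are taken before rounding.

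**A wider grid.** With Kaplan-Meier mortality of 20% to 40% and exits of 1% to 3% per year, the understatement is 0.4 to 6.1 points for r from 1.5 to 3, and the overstatement is 0.5 to 2.3 points for r = 0.5.

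**Against sampling error.** The Greenwood-type variance is S² × h[exp((h+c)T) − 1]/[(h+c) × 150], with S = exp(−hT). Case A: 0.6 × 0.6487/150 = 0.002595; square root 0.0509; times 0.7408 and 1.96 gives a half-width of 7.4 points. Case B by the same steps: 8.7 points. Over the wider grid the half-width is 6.6 to 8.5 points.

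**Extreme bounds, Case A.** Counting every leaver as alive at year 10 gives 0.03/0.05 × (1 − exp(−0.5)) = 23.6%; counting every leaver as dead gives 23.6% + 15.7% = 39.3%.

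**The case against.** The contact procedure is a floor, not a ceiling, and it includes a third party: "Should telephone, e-mail and mail efforts to contact the subject be unsuccessful, the subject's primary physician should be contacted". Together with the missed-visit rule in 8.11, it may reveal a death before closure. That stands, and it lowers the likely number of missed deaths. It does not reach deaths after closure or after withdrawal.

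A reader might infer that reported mortality will be too low. The documents do not support a direction: they give no hazard for leavers, and healthier leavers would reverse the sign. A reader might also infer that the results would hide the problem altogether. That goes too far. SAP 7.1.1 tabulates withdrawn and lost subjects, SAP 7.2 gives numbers at risk, and SAP 7.4 reports the number analysed. These show how much follow-up is missing and allow rough bounds, though they cannot measure the bias.

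It is fair to add that 10-year mortality is descriptive, that censoring at discontinuation is conventional, and that under moderate assumptions the bias is smaller than the confidence half-width. All three stand. But the bias is systematic, and the interval does not reflect it.

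Finally, the Monitoring, Data Management and Safety Plans and the consent form were not available. A vital-status step could be in one of them, so the claim is that none is described in the protocol or SAP, not that none exists.

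**Conclusion.** The point holds as a cheap improvement to long-term data. As written, annual Kaplan-Meier mortality to year 10 is unbiased only under equal mortality in leavers and stayers, and the planned data cannot test that. With death at 3% and loss at 2% per year, the understatement is about 1.0 to 3.4 points for leaver hazards of 1.5 to 3 times. Reaching about 8 points needs 5% death, 4% loss and triple mortality together. Equal hazards give no bias. All of these rates are assumptions.

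The point should not be read as a threat to the primary results: both primary endpoints are assessed within about 30 days, where little loss is expected.

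**What to change.** **Protocol 8.15.** Before a subject is closed as lost, and again before the final report for every lost or withdrawn subject who has not refused, the site checks vital status in medical records and public death records. It enters alive, dead or unknown, with date and source, in the eCRF. At withdrawal, record whether the subject stops visits only or also refuses record checks. The same check can cover explanted and never-implanted subjects, whom Protocol 8.5 follows for only 30 days, because mortality is analysed in the attempted implant set.

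**SAP 7.9.3 item 1.** Use these data for all-cause mortality only.
- Count deaths at the date of death.
- Censor subjects confirmed alive at the date last known alive.
- State one rule, applied to all searched subjects, for those with no death record found. For example, censor at the search cut-off date in the main analysis, with a sensitivity analysis censoring at last contact. The first leans low if the search misses deaths. The second leans high, because found deaths count while the others' later survival does not. Without a stated rule, ascertainment would depend on the outcome.
- Censor refusers at withdrawal.

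Keep all other outcomes censored as planned.

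**Cost.** A records search for roughly 24 to 40 subjects under the two cases above, at sites that are all in the United States; possibly one consent sentence; and possibly a slightly higher reported mortality. No visit, procedure or primary analysis changes.
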